Two-sided 95% confidence intervals will be provided for primary and secondary endpoints defined by proportions. Confidence intervals will also be calculated for differences between pre-defined groups of patients, if appropriate (e.g. LCIG as monotherapy vs. LCIG plus add-on therapy).

Logistic regression and subgroup analyses will be applied to investigate the impact of potential prognostic factors for LCIG monotherapy. Potential prognostic factors used for the regression model will include demographic variables (ie. age, gender, race) and baseline disease characteristics at LCIG initiation (PD duration, hours of OFF time, hours of dyskinesia, Levodopa equivalent daily dosage).

Details of statistical methods will we presented in a separate statistical analysis plan (SAP). All statistical analyses will be carried out by means of the SAS® package (version 9.4 or higher).

9.8 **Quality Control**

The personnel at each PMOS site may be trained on the protocol and PMOS procedures by a CRA at a site training visit, via telephone or on-site.

Throughout the PMOS, the CRO and AbbVie will periodically follow-up with sites to ensure that SAEs and PCs are being reported.

All PMOS data will be entered into the eCRF which will be accessed via a web-based EDC system. Any necessary corrections will be made to the database and documented via queries, source data clarification form or audit trail. A manual review of elected line listings will also be performed at the end of the PMOS. A clinical monitor working on behalf of AbbVie will perform a final site closure visit when the site or study is closed.

9.9 **Limitations of the Research Methods**

The primary limitation of this PMOS is that it is performed in an open-label, noncontrolled and non-randomized design with mainly retrospective data capturing. Thus, selection and reporting bias cannot be excluded. In order to minimize these biases, all eligible patients shall be enrolled in a consecutive manner.

Moreover, as only patients on current LCIG therapy are included, data of patients who discontinued treatment will not be collected. Therefore, comprehensive safety conclusions may not be drawn from the study results.

Finally as the study aims to identify treatment predictors based on patient's and physician's profiles; however it can be influenced by LCIG country specific prescription or reimbursement status. Therefore, country origin would be taken into account when analyzing treatment predictors.

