#### 2.5 Quality control

The SAP is consistent with the underlying study protocol. If there is a need for deviating substantially from the protocol-defined analysis, this is described in detail. The methods described in this SAP are mandatory for statistical programming.

Quality control (QC) of statistical programming will be performed according to the QC plan, which specifies all planned actions to ensure that the performed analyses are correct, traceable and in line with the planned analysis as specified in the SAP. The QC plan also includes filing of statistical programs, outputs and documentation of QC. It is finalized by the project statistical programmer before the start of any programming activities.

Documentation of QC is filed in the trial master file.

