#### Symptoms related to treatment

Separately for 'immediately prior to LCIG initiation' and 'visit':

- Number of symptoms related to treatment
- Number of symptoms related to treatment in appropriate categories
- Hypersexuality (yes, no, unknown)
  - o If yes: Severity

Frequency

- Compulsive shopping (yes, no, unknown)
  - o If yes: Severity

Frequency

- Gambling (yes, no, unknown)
  - If yes: Severity

Frequency

- Binge Eating (yes, no, unknown)
  - If yes: Severity

Frequency

- Punding (yes, no, unknown)
  - o If yes: Severity

Frequency

- Dopamine Dysregulation syndrome (yes, no, unknown)
  - If yes: Severity

Frequency

Other (yes, no)

 Total number of symptoms calculated as sum of the number of motor symptoms, number of non-motor symptoms and number of symptoms related to treatment

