#### 7.8 Regression analyses

For the application of regression analysis, missing/unknown data for prognostic factors are imputed. Imputation is planned to be accomplished by a regression based single imputation method where missing values of one predictor variable are predicted by regression models with a set of remaining potential prognostic variables as independent variables. This might require adequate preprocessing of the data. Modification of this imputation strategy is possible if implied by the data.

Regression analyses will be evaluated for FAS and conducted on imputed data.

Regression analyses will be performed separately for each of the two primary variables (see Section 6.4):

LCIG monotherapy 1 (LCIG monotherapy 2, respectively) at 12 months after LCIG initiation will be used as dependent (i.e. response) variable in two multivariable logistic regression models. The independent variables (i.e. potential predictors) will be checked for collinearity.

For the first multivariable logistic regression model the following variables will be considered as potential predictors (i.e. independent variables):

Table 7-2: Potential predictors used for regression analysis 1

Variable	Range	Dichotomization/Grouping
Age	numeric	-
Gender	Male, Female	Male vs. Female
Race	White, Black, Asian, Mixed, Other	White vs. Non-White
Education	No formal education, primary school, secondary school, non-university professional education, university	Less than secondary school vs. secondary school or higher
Total number of symptoms	numeric	
Number of symptoms related to treatment	numeric	
Number of motor symptoms	numeric	-
Number of non-motor symptoms	numeric	-
Total daily LEDD at LCIG initiation	numeric	-
Time from PD diagnosis to start of LCIG	numeric	-
Duration of 'Off' state time during a 24h period	numeric	-
Duration of dyskinesia during a 24h period	numeric	-
UPDRS V prior to LCIG initiation (if available)	numeric	-
Any device aided therapy other than LCIG in the past	Yes, No	Yes vs. No
Any dopamine agonists in the past	Yes, No	Yes vs. No
PD motor phenotype	Tremoric, Akinetic rigid, Mix	
Time from PD diagnosis to motor fluctuation	numeric	
Time from PD diagnosis to onset of morning akinesia	numeric	
Country		
GNI	numeric	

Categorical predictors will be dichotomized / grouped as shown in Table 7-2 in order to simplify interpretation.

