Backward elimination with a significance level of 0.05 will be applied to stepwise automatically select relevant predictors. Effect estimates and p-values will be given for each (potential) predictor.

For the second multivariable logistic regression model the following variables will be considered as potential predictors (i.e. independent variables):

Table 7-3: Potential predictors used for regression analysis 2

Variable	Range	Dichotomization/Grouping
Approximate number of APD patients treated per year	numeric	-
Years of LCIG experience	numeric	-
Years of DBS experience	numeric	-
Approximate number of APD patients treated with LCIG per year	numeric	-
Number of years physician has been working at the institution	numeric	-
Average number of PD and APD patients per year at center	numeric	-
Number of specialist physicians working with PD patients at center	Numeric	-
Origin of service at center	National health services, Private health services	National health services vs. Private health services
Average frequency of routine visits for APD patients on device aided therapy at center	< 1x/year, 1x/year, 2x/year, 3x/year, > 3x/year	≤ 1x/year vs. ≥ 2x/year
Country		
GNI	numeric	

Categorical predictors will be dichotomized / grouped as shown in Table 7-3 in order to simplify interpretation.

Backward elimination with a significance level of 0.05 will be applied to stepwise automatically select relevant predictors. Effect estimates and p-values will be given for each (potential) predictor.

For both regression models the Gross National Income (GNI) is defined as follows (source: https://data.worldbank.org/indicator/NY.GNP.PCAP.CD):

Country	GNI
Austria	45.44
Bulgaria	7.76
Canada	42.87
Czech Republic	18.16
Croatia	12.43
Estonia	18.19

Greece	18.09
Hungary	12.87
Ireland	55.29
Israel	37.27
Netherlands	46.18
Romania	9.97
Spain	27.18
Sweden	52.59

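### SAP 7.8 picks predictors of monotherapy by backward elimination at 0.05 from 20 and 11 candidates with no intervals, validation or caveat, so noise predictors are likely if few candidates matter

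*SAP*

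**What the plan says.** Protocol 9.7 names seven factors for the logistic regression: "Potential prognostic factors used for the regression model will include demographic variables (ie. age, gender, race) and baseline disease characteristics at LCIG initiation", the latter being "PD duration, hours of OFF time, hours of dyskinesia, Levodopa equivalent daily dosage". Details are left to the SAP. Protocol 9.9 adds that country is to be considered in the predictor analysis.

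SAP 7.8 introduces Table 7-2 (20 rows) with "For the first multivariable logistic regression model the following variables will be considered as potential predictors (i.e. independent variables". It gives 11 physician, site and country rows in Table 7-3 for a second model. Both models are fitted to monotherapy 1 and to monotherapy 2 at 12 months, so there are four regressions. The selection rule is the same in both models: "Backward elimination with a significance level of 0.05 will be applied to stepwise automatically select relevant predictors". Effect estimates and p-values are to be given for each potential predictor.

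A collinearity check is planned, without a threshold or an action. SAP 7.1 plans confidence intervals for proportions only. SAP 7.10 calls the study exploratory and leaves changes to the analyses open.

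**The concern.** Finding predictors of long-term monotherapy is a stated secondary objective (Protocol 8.0, SAP 3.2), and the factors that survive elimination are called relevant predictors. A factor survives only if its p-value is below 0.05, so the printed p-value of a survivor no longer measures evidence on the usual scale. Its odds ratio is reported only when it happens to be large enough. With many candidates and few events per parameter, the final list can contain noise, and nothing in the planned output would let a reader see how stable it is.

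**Working it through.** **The plan's own design figure.** The only computed figure is the sample size for precision: 1.96² × 0.25 / 0.05² = 384.15, rounded up to 385, as Protocol 9.5 states. Neither document gives an error rate for the regression.

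**Parameters in Table 7-2.**
- 18 rows with one parameter each, motor phenotype ("Tremoric, Akinetic rigid, Mix", no grouping) with 2, and country with 13 for the 14 countries in the GNI table: 18 + 2 + 13 = 33.
- Two exact dependencies. First, "Total number of symptoms calculated as sum of the number of motor symptoms, number of non-motor symptoms and number of symptoms related to treatment" (SAP 6.3), and all three components are also candidates. Second, "For both regression models the Gross National Income (GNI) is defined as follows", with one fixed value per country, so GNI adds nothing once country is in.
- If country is kept: 33 − 2 = 31 parameters. If GNI is kept instead: 33 − 1 − 13 = 19. Either way 20 − 2 = 18 effects are tested.
- Table 7-3: 11 − 1 = 10 effects; with country, 9 + 13 = 22 parameters.

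**Events per parameter.** Assume 36-40% on monotherapy (the registry figure in Protocol 7.0) and 385-400 patients: 0.36 × 385 = 139 to 0.40 × 400 = 160 events.

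| Model | Parameters | Events per parameter |
|---|---|---|
| Table 7-2, country kept | 31 | 4.5-5.2 |
| Table 7-2, GNI kept | 19 | 7.3-8.4 |
| Table 7-3, country kept | 22 | 6.3-7.3 |
| Protocol 9.7 factors plus country | 7 + 13 = 20 | 7.0-8.0 |

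**Chance of at least one false predictor when nothing is predictive.** For k independent effects this is 1 − 0.95^k.
- Table 7-2: 1 − 0.95^18 = 60.3%.
- Table 7-3: 1 − 0.95^10 = 40.1%.
- The seven Protocol 9.7 factors: 1 − 0.95^7 = 30.2%; with country, 1 − 0.95^8 = 33.7%.

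**Simulation of the elimination itself** (400 patients, 14 countries, Wald tests, no missing data).
- Table 7-2, no true predictor: with equal country sizes and 1,500 runs per setting, at least one factor is kept in 58.6%, 58.3% and 57.2% of runs at outcome rates of 0.25, 0.38 and 0.50. It is 58.9% if GNI replaces country. About 0.9 false predictors are kept on average. A separate simulation with countries of 10-60 patients (1,000 runs, 38% events) gave 60%.
- Table 7-3, no true predictor: 39.6-41.5% if sites do not differ. It is 64-68% if sites do differ and the model ignores it (assumed SD 0.5 on the logit scale, 49 sites).
- One true predictor in Table 7-2: 57-58% of runs still keep a false one. With three true predictors of OR 1.25 per SD (600 runs): 54%.
- Size of kept effects: a true OR of 1.25 per SD averages 1.34 when kept (kept in 59% of runs), and 1.38 in the three-predictor setting. A true OR of 1.40 averages 1.44 (kept in 89%).

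**The case against.** A reader might infer that the SAP replaces the protocol's factor list without declaring it, since SAP 2.5 says "The SAP is consistent with the underlying study protocol". The documents do not support that. All seven factors remain in Table 7-2, with PD duration as time from diagnosis to LCIG start, and Protocol 9.7's list is not exhaustive. The secondary endpoints in Protocol 4.0 and 9.1 call for predictors from socio-demographics, motor and non-motor symptoms, PD medication and the physician's profile. Most of the added rows carry out that endpoint, and country is foreseen in Protocol 9.9. For the same reason, a model limited to the seven factors should not displace the wider ones.

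A reader might also infer that three in five of all the planned regressions would report noise. That holds only for Table 7-2 with no or almost no true predictors. With eight noise effects left, the formula gives 34%.

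Nor does elimination itself create the error rate. With seven factors, elimination and the full model give nearly the same figure (29.9% and 30.6%), so the rise to about 60% comes from the number of candidates.

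The overstatement of odds ratios is modest, and part of it is small-sample bias from fitting many parameters. For the one true predictor simulated, ordinary 95% intervals still covered the true value in about 97% of the runs that kept it.

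Finally, the SAP calls the study exploratory, and its reporting sentence need not be limited to the factors that survive. Both points stand. But the exploratory label does not supply an interval, a stability measure or a warning, and an unqualified p-value beside a selected factor will be read as a test.

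**Conclusion.** The concern holds as a weakness of the planned predictor analysis. If few candidates matter, about 57-60% of Table 7-2 analyses, and about 40% of Table 7-3 analyses if sites do not differ, would present at least one noise factor as relevant. Weak true effects would be overstated by roughly 7-10% on the odds ratio scale (1.34/1.25 = 1.07; 1.38/1.25 = 1.10), strong ones by about 3% (1.44/1.40 = 1.03). These figures assume largely independent candidates, 38% events unless stated otherwise, and complete data. The 36-40% registry rate is an assumption here: it refers to patients without additional oral PD medication, and monotherapy 2 allows evening medication, so its rate may differ. The weakness concerns a secondary, exploratory objective. It is not an undeclared deviation from the protocol, and it leaves the primary percentages untouched.

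**What to change.** In SAP 7.8:
1. Before selection, remove the total symptom count and state which one of country and GNI stays.
2. For each outcome, report a pre-specified model without selection, with odds ratios and 95% intervals: the Protocol 9.7 factors plus country. The sponsor may add the three symptom counts and the two past-therapy rows, which the protocol endpoint covers. That would make 20 + 5 = 25 parameters, or 139/25 to 160/25 = 5.5-6.4 events each.
3. Keep the backward models for Tables 7-2 and 7-3 as exploratory, report how often each factor is retained in bootstrap resamples, and state that their p-values are not tests.

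The cost is SAP wording, one extra model per outcome and a bootstrap loop. Fewer factors will be called significant. The fixed model does not remove multiplicity: if nothing is predictive, the chance of at least one nominally significant factor is still about 30-34%, or 1 − 0.95^13 = 49% with the five optional rows.

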9.5 Study Size

The primary objective of this PMOS is to estimate the percentages of APD patients on LCIG monotherapy right after LCIG initiation and at 3, 6, 9, and 12 months, respectively.

Sample size calculation was based on pre-defined precision of the estimators, expressed as the maximum length of the corresponding two-sided 95% confidence intervals. In order to achieve a precision of \pm 5% (i.e. the confidence intervals are not wider than 10%), and considering an underlying percentage of 50% (i.e. the percentage which leads to the largest sample size), at least 385 (evaluable) patients are necessary.

In this PMOS, only a small number of non-evaluable patients are expected. Therefore, it is planned to include a total number of approximately 400 patients.

9.6 **Data Management**

CRFs must be completed for each patient enrolled in this PMOS. These forms will be used to transmit information collected during the PMOS to AbbVie and regulatory authorities, as applicable. The CRF data for this PMOS are being collected with an electronic data capture (EDC) system, Rave[®], provided by the technology vendor Medidata Solutions Incorporated, NY, USA. The EDC system and the PMOS-specific eCRFs will comply with Title 21 CFR Part 11. The documentation related to the validation of the EDC system is available through the vendor, Medidata, while the validation of the PMOS-specific eCRFs will be conducted by AbbVie and will be maintained in the Trial Master File at AbbVie. The investigator will document patient data in his/her own patient files. Questionnaires filled in by the patients will be source data (e.g., QUIP-RS, PDQ-8, PDSS-2, BMQ). All eCRF data required by this protocol will be recorded in the EDC system. All data entered into the eCRF will be supported by source documentation, except for questionnaires that are completed by the physicians

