## 3.2 Secondary objectives

The secondary objectives of this study are:

- To describe PD medication management, and the main reasons justifying their use, directly prior to LCIG initiation, at LCIG initiation and during long-term LCIG treatment
- To describe LCIG infusion settings and substantial dose adjustments and the respective reasons
- To describe the Healthcare Resource Utilization (HCRU)
- To identify the physician's and patient's/caregiver's overall preference for the pharmacological treatment approach using LCIG as monotherapy vs. LCIG plus add-on PD medication
- To identify predictors for achieving long-term monotherapy with LCIG vs. LCIG plus add-on PD medication, based on the patient's profile and the physician's profile
- To describe the latency from LCIG initiation until LCIG is given as a monotherapy and the average duration of LCIG monotherapy
- To describe the latency from the initiation of LCIG therapy until the introduction or tapering of each PD medication, or until substantial dose adjustments of LCIG
- To evaluate the percentage of patients who are on LCIG monotherapy, PD medication management and HCRU for the participating countries who have enrolled a minimum of 20 study subjects

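### Regression model 2 relates physician and centre factors to monotherapy without any patient characteristic, so case mix within a country can pass for a physician or service-type effect

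*SAP*

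**What the plan says.** SAP 3.2 sets a secondary objective of finding predictors of long-term monotherapy "based on the patient's profile and the physician's profile". SAP 7.8 serves it with separate models: monotherapy (definition 1 or 2) "at 12 months after LCIG initiation will be used as dependent (i.e. response) variable in two multivariable logistic regression models".

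- **Model 1 (Table 7-2)** holds patient variables plus Country and GNI, and no physician or centre variable.
- **Model 2** is introduced with "For the second multivariable logistic regression model the following variables will be considered as potential predictors". Table 7-3 holds physician and centre variables plus Country and GNI, and no patient variable.

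Both models use backward elimination at 0.05. No model combining the two sets is named, and nothing says that Country or GNI stays in.

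Protocol 9.7 states that the factors for the regression model will include age, gender and race, together with "baseline disease characteristics at LCIG initiation (PD duration, hours of OFF time, hours of dyskinesia, Levodopa equivalent daily dosage". Protocol 9.9 adds that country should be taken into account when predictors are analysed.

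**The concern.** The outcome belongs to the patient, and patients are not allocated to physicians at random. High-volume or long-experienced centres, or one type of health service, may treat people with longer disease, more OFF time or heavier prior medication. Those features plausibly bear on whether add-on drugs can be stopped. With no patient variable in the model, any such difference is credited to the physician or centre factor, and elimination at 0.05 may then retain that factor as a relevant predictor.

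Country and GNI, if they survive elimination, absorb differences between countries. They cannot absorb differences between centres in one country. The physician half of the predictor objective is at stake; the primary percentages are not affected.

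**Working it through.** **Plan's own figure.** Protocol 9.5 asks for precision such that "i.e. the confidence intervals are not wider than 10" per cent, "considering an underlying percentage of 50" per cent. n = 1.96² × 0.5 × 0.5 / 0.05² = 384.15, rounded up to 385. This matches "at least 385 (evaluable) patients are necessary". The plan then says "it is planned to include a total number of approximately 400 patients". The figure is correct but says nothing about the regressions.

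**Row count, Table 7-3.**
- Physician (5): APD patients per year, years of LCIG experience, years of DBS experience, LCIG patients per year, years at the institution.
- Centre (4): PD/APD volume, number of specialists, origin of service, visit frequency.
- Country and GNI (2).
- Patient characteristics: 0 of 11.

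**Size, first simulation.** Assumptions: N = 400, 38% events (midpoint of the 36-40% registry range in protocol section 7.0), and a null physician factor correlated r with an omitted severity score. The model is univariable, without Country or GNI.
- r = 0.1: significant in 6-10% of studies.
- r = 0.2, severity OR 0.6 per SD: apparent OR 0.91, significant in 16%.
- r = 0.3, severity OR 0.5 per SD: apparent OR 0.82, significant in 45%.

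An independent repeat gave 17% and 43% for the last two. With the severity score in the model the rate was 3-5%.

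**How large can r be?** A factor fixed within a centre has r = (centre-level correlation) × √(share of severity variance lying between centres).
- Share 10%: r = 0.2 needs 0.2/√0.10 = 0.63; r = 0.3 needs 0.3/√0.10 = 0.95.
- Share 20%: r = 0.3 needs 0.3/√0.20 = 0.67.
- Share 5%: r cannot exceed √0.05 = 0.22.

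So r = 0.3 is an upper-end case.

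**Size, second simulation, country kept.** Assumptions: N = 400; 30, 50 or 75 sites in 14 countries; 600 runs per setting; a null centre factor. Ranges are across the three site counts.

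| Between-centre share | Centre-level correlation | Severity OR per SD | Implied r | Significant, no patient covariate | Median OR per SD | Significant, severity added |
|---|---|---|---|---|---|---|
| 10% | 0 | 2.0 | 0 | 5.7-7.0% | 0.99-1.00 | 4.3-6.5% |
| 10% | 0.5 | 1.5 | 0.16 | 7.7-9.7% | 0.93-0.94 | 4.5-6.2% |
| 10% | 0.5 | 2.0 | 0.16 | 12.8-16.7% | 0.89-0.90 | 5.5-6.2% |
| 20% | 0.5 | 2.0 | 0.22 | 18.3-26.3% | 0.86-0.87 | 4.8-5.7% |
| 20% | 0.7 | 2.0 | 0.31 | 27.7-40.7% | 0.81-0.82 | 5.8-6.5% |

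The Monte Carlo standard error at 5% is √(0.05 × 0.95/600) = 0.9 points. With zero correlation the country-adjusted rate is close to nominal, so the excess in the lower rows comes from case mix. If country is dropped, the correlated settings give 12-46%. Not all of that excess is case mix, because dropping country already gives 9-13% at zero correlation.

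Neither simulation runs the backward elimination or the full predictor list. The adjuster here is the whole confounder; real covariates would remove only part of the bias.

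**Cost in parameters.** Assume 38% events, so 400 × 0.38 = 152, and Country as 13 indicators (14 countries in the SAP's GNI table). GNI then adds nothing, since it is one value per country. Model 2 starts with 9 + 13 = 22 parameters: 152/22 = 6.9 events each. With six adjusters, 152/28 = 5.4; with seven, 152/29 = 5.2.

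**The case against.** The protocol lists patient-profile and physician-profile predictors as separate endpoints, and Tables 7-2 and 7-3 follow that split. The aim is to identify predictors in an exploratory study, and nowhere do the documents claim an independent or causal physician effect. A marginal predictor needs no case-mix adjustment. Some adjusters, such as disease duration at LCIG start, may partly reflect when the physician chooses to offer LCIG, so adjusting could remove part of a real association. SAP 7.10 also allows extensions if the data call for them.

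Much of this stands. It is a good reason to keep the unadjusted model and report both versions. It does not remove the need for the adjusted one, because a marginal association cannot show whether the factor or the patients account for it. SAP 7.10 commits to nothing, and an adjustment chosen after seeing results is weaker than one fixed beforehand.

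Two stronger readings are tempting. A reader might infer that the SAP plainly breaches protocol 9.7. But 9.7 speaks of one regression model, and model 1 does carry the named kinds of factor. What can be said is that model 2 carries none of them, and that SAP 2.5, which undertakes to describe substantial deviations, contains no explanation. A reader might also infer that model 2 has a 45% false-positive rate, or that any physician factor it retains is spurious. The documents give no number of sites, between-centre variance or correlation with case mix, so neither follows.

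**Conclusion.** The point holds as a gap in interpretability. As specified, model 2 cannot separate a physician or service-type association from case mix within a country. The bias cannot be sized from the documents. Under the assumptions shown, the false-positive rate for a null factor runs from near nominal (about 6-10% at weak correlation) to about 40-45% in an upper-end case, and it could be small in practice. The sample size of 385 and the primary estimates are unaffected.

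**What to change.** Keep model 2 as planned. Pre-specify a second, adjusted version that adds these terms, exempt from elimination:

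- age, gender and race (White vs. Non-White);
- time from PD diagnosis to LCIG start;
- OFF hours and dyskinesia hours immediately prior to or at LCIG initiation (SAP 6.3).

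If LEDD is added, derive it from the PD medication recorded right before LCIG (protocol 9.2.7.5). Do not use the Table 7-2 LEDD at LCIG initiation: SAP 6.5 defines LEDD under add-on medication from initiation onwards, so it reflects add-on load and sits close to the outcome. The SAP's analysis variables define no pre-LCIG LEDD, so this one has to be built.

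Report physician and centre effects with and without adjustment, and note that some adjusters may partly reflect physician practice.

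The cost is one more run for each monotherapy definition on data already collected. Six or seven extra parameters mean fewer events per parameter, as shown in the working, and wider intervals.

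### SAP 7.8 lists predictors that are exact functions of others without saying which one goes, and leaves country open to backward elimination

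*SAP*

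**What the plan says.** SAP 7.8 plans two multivariable logistic models for monotherapy at 12 months, each run for both monotherapy definitions. Table 7-2 lists 20 patient-side candidates and Table 7-3 lists 11 physician- and centre-side candidates. Country and GNI appear in both tables.

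- **GNI:** "For both regression models the Gross National Income (GNI) is defined as follows", followed by a table of 14 countries with one number each.
- **Symptoms:** Table 7-2 lists the motor, non-motor and treatment-related symptom counts and also their total, which SAP 6.3 defines as "calculated as sum of the number of motor symptoms, number of non-motor symptoms and number of symptoms related to treatment". Table 7-3 has no symptom rows.
- **Collinearity:** "The independent variables (i.e. potential predictors) will be checked for collinearity". No criterion is given, and no rule for what follows.
- **Selection, both models:** "Backward elimination with a significance level of 0.05 will be applied to stepwise automatically select relevant predictors". No variable is exempt.
- **Reporting, both models:** "Effect estimates and p-values will be given for each (potential) predictor".
- **Coding:** "Categorical predictors will be dichotomized / grouped as shown in Table 7-2 in order to simplify interpretation", with the same statement for Table 7-3. The range and grouping cells for Country are blank in both tables.

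Protocol 9.9 says that country-specific prescription or reimbursement status can influence the predictor analysis, and concludes that "country origin would be taken into account when analyzing treatment predictors". It gives no method.

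**The concern.** There are two linked gaps.

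First, some candidates are determined by others before any data are seen. Once Country is in as a class variable, GNI carries no further information. The symptom total carries none beyond its three parts. The likelihood then has no unique maximum, so an analyst must remove something. The SAP does not say what, and the choice has consequences. Removing GNI keeps full adjustment for country. Removing Country leaves one linear income term in place of 13 degrees of freedom.

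Second, the protocol names country in advance as an influence on the predictor analysis, yet the SAP retains it only if it is significant. A 13-df term in about 400 patients can miss 0.05 while countries still differ. Patient or physician factors that vary between countries could then stand in for prescribing or reimbursement rules. Identifying predictors of long-term monotherapy is a listed secondary objective.

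**Working it through.** **The plan's own figure.** Protocol 9.5 sizes the study for a 95% interval of ±5 points at 50%: n = 1.96² × 0.5 × 0.5 / 0.05² = 384.15, rounded up to 385, with about 400 planned. This reproduces. No size is given for the regressions.

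**Columns and rank.** Take Country as 13 indicators (the 14 countries of the GNI table) and motor phenotype as 2 indicators (three levels). Every other row takes one column.

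- Model 1: 1 intercept + 18 single-column rows + 2 + 13 = 34 columns.
- Model 2: 1 intercept + 10 single-column rows + 13 = 24 columns.

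Design matrices with the SAP's GNI values, the symptom total set to the sum of its parts, other predictors simulated and N = 400 gave:

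| Candidate set | Columns | Rank |
|---|---|---|
| Model 1 as listed | 34 | 32 |
| Model 1 without GNI | 33 | 32 |
| Model 1 without GNI and symptom total | 32 | 32 |
| Model 2 as listed | 24 | 23 |
| Model 2 without GNI | 23 | 23 |

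Model 1 therefore has two exact dependencies and model 2 has one.

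**What this does to the first elimination step.** The df of a row's test is the rank of the full set minus the rank without that row. GNI gets 0 df in both models. In model 1 each of the four symptom rows also gets 0 df, because any one of them follows from the other three. So 5 of 20 rows in model 1 and 1 of 11 in model 2 have no p-value to compare with 0.05. Country keeps a test, on 12 df while GNI is present. In a plain maximum-likelihood fit on simulated data, full model 1 did not converge (largest standard error about 2 million). Full model 2 was reported as converged, although its Country and GNI coefficients are not uniquely determined.

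**How often country would go.** Inputs: N = 400, 40% on monotherapy (upper end of the registry's 36-40% cited in the protocol), 14 countries, and country effects normal on the logit scale with an assumed SD. Test: 2 × (log-likelihood with country − log-likelihood without), compared with chi-square on 13 df at 0.05; 4,000 simulated studies per setting. In the unequal case four countries hold 25%, 20%, 15% and 10% of patients, and ten hold 3% each. The documents give neither the SD nor the country sizes. To show what each SD means, the 10th and 90th percentile country rates are expit(logit 0.40 ± 1.2816 × SD).

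| SD | 10th-90th percentile country | Not significant: equal sizes | Unequal sizes |
|---|---|---|---|
| 0.2 | 34%-46% | 82% | 81% |
| 0.3 | 31%-49% | 61% | 62% |
| 0.4 | 29%-53% | 37% | 42% |
| 0.5 | 26%-56% | 18% | 25% |
| 0.7 | 21%-62% | 3% | 7% |

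**What losing country does to a predictor.** A predictor with no true effect was simulated in 399 patients from 14 countries of 10 to 47, with SD 0.3 to 0.5, country dropped when not significant, and 1,000 runs per setting. False-positive rates at 0.05, as ranges over two independent sets of runs:

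| Predictor | Country by elimination | Country forced |
|---|---|---|
| 5% of variance between countries | about 5-6% | about 5-6% |
| 20% between countries | about 5-9% | about 5-6% |
| 50% between countries, correlated 0.5 with country effects | about 12-14% | about 5-6% |

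**The case against.** **A collinearity check is planned.** It would find an exact dependency at once, and removing one variable per dependency restores full rank. This stands against a reading that the models cannot be fitted at all. It does not close the gap, because the SAP has no rule for which variable goes.

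**Exactness depends on coding.** Country's coding is blank. If countries were pooled into broader groups, GNI would no longer be an exact function of Country. The regression-based single imputation in SAP 7.8 could also break the exact symptom sum in imputed records and leave near-collinearity. Both points stand. The first is itself something the SAP should settle.

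**The protocol promises no forced term.** Its wording is general, and listing Country and GNI as candidates can be said to take country into account. A reader might infer that the SAP breaches a protocol commitment. The documents do not support that; they show that the final models may end without country, and nothing prevents it.

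**The study is exploratory.** SAP 7.10 allows unrestricted changes, and no primary percentage depends on these models. That limits the weight of the point. But SAP 2.5 makes the SAP's methods binding for programming, and freedom to choose among redundant variables after seeing the data is the difficulty, not its cure.

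**Non-significance of country is not bias.** This stands. A reader might infer that the reported predictors will be confounded. The last table shows little effect unless a predictor is strongly clustered by country and related to the country effects.

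**Forcing country has a price.** Table 7-3 holds only physician- and centre-level predictors. Fixed country effects leave within-country contrasts, which may be thin where a country has few sites. This also stands and shapes the fix.

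**Conclusion.** The concern holds in a bounded form. As listed, model 1 has two exact dependencies (GNI on Country; the symptom total on its parts) and model 2 has one (GNI on Country). The GNI dependency assumes that Country is entered as an unpooled class variable. A reader might infer that the symptom redundancy affects both models, but Table 7-3 contains no symptom rows. Separate estimates and p-values for every candidate cannot come from the full sets, and the SAP does not say how to resolve this.

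Country is not secured in the final models. With assumed log-odds SDs of 0.3 to 0.5, it would fail the 0.05 criterion in roughly 60% to 20% of studies; at 0.7 or more this is rare. The consequence is conditional: small for most predictors, with false positives about doubled for one that is strongly country-clustered and correlated with the country effects. The primary percentages are unaffected. The change is worth making before analysis because it is cheap and the dependencies are known in advance.

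**What to change.** In SAP 7.8:

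1. State how Country is coded. Keep it in both models, outside the elimination step. A random intercept is preferable in model 2, where predictors are at physician or centre level; a fixed effect or random intercept would serve in model 1.
2. Remove GNI from Tables 7-2 and 7-3. If it is of interest, fit it in a separate model with a random country intercept.
3. Delete the symptom total from Table 7-2 and keep its three components.

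Both sets then have full rank with Country as indicators (32 of 32 and 23 of 23), and country cannot be eliminated. The direct cost is SAP wording only. The statistical cost is wider intervals for predictors that vary mainly between countries, possibly noticeably wider for centre-level predictors in countries with few sites. That loss has not been quantified, since the documents do not give sites per country.
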